8.3.7 Central Laboratory Assessments

...

For pathfinderTM2 main phase: All blood samples including genotyping blood sample will be destroyed after finalisation of the trial report. Blood samples of patients who are suspected of inhibitors or who have developed inhibitors will be stored at least until evaluation of the clinical trial data by the authorities in the patient's country.

For pathfinderTM2 extension phase: Laboratory samples will be destroyed after trial completion

If allowed by local law and consented to, in pathfinderTM2 extension phase addendum 'Storage of blood samples from pathfinderTM2', samples drawn for analysis of antibodies in pathfinderTM2 main and extension phase will be stored until market authorisation in case further characterisation of the samples should be required by authorities.

9 Trial Supplies

9.3 Packaging and Labelling of Trial Product(s)

Novo Nordisk A/S will ~~label and pack the~~ be responsible for labelling and packaging of the trial product. *Third party vendors may be employed.*

12 Adverse Events, Technical Complaints and Pregnancies

12.1 Definitions

...

Serious Adverse Event (SAE):

- Important medical events ^{d)} that may not result in death, be life-threatening ^{a)} or require hospitalisation may be considered a SAE when, based upon appropriate medical judgement, they may jeopardise the patient and may require medical or surgical intervention to prevent one of the outcomes listed in this definition. *Suspicion of transmission of infectious agents via the trial product and formation of inhibitory antibodies must always be considered a SAE.*

18 Statistical Considerations

18.2.4.1 PK Endpoints

- *FVIII activity 30 min post-injection (C_{30min})*

...

All pharmacokinetic endpoints will be modelled and analysed by an ANOVA on the log transformed parameter by visit. Estimates of each endpoint with 95% confidence intervals will be provided back-transformed to the natural scale. *In addition, the 90% confidence intervals will be provided back-transformed to the natural scale for AUC and C_{30min}.*

18.10 Analyses of Extension Phase Data

...

Data from part 2 of the Extension Phase

All safety parameters except Adverse Events and Serious Adverse Events, will in Extension Phase Part 2 be presented by listings and individual graphical representation only.

All *other* evaluations/summaries based on accumulated data in part 1 will be repeated in part 2, accumulating data from the entire trial (Main Phase + Extension Phase part 1 + part 2).

Protocol Amendment
Trial ID: NN7088-3859
UTN: U1111-1119-7416
EudraCT No.: 2011-001142-15

~~CONFIDENTIAL~~

Date:
Version:
Status:
Page:

29 April 2016 | **Novo Nordisk**
2.0
Final
1 of 10

Protocol Amendment
no 19
to Protocol, final version 11
dated 29 November 2013

Trial ID: NN7088-3859

pathfinder™ 2

**A Multi-national Trial Evaluating Safety and Efficacy, including Pharmacokinetics, of
NNC 0129-0000-1003 when Administered for Treatment and Prophylaxis of Bleeding in
Patients with Haemophilia A**

Trial phase: 3

Applicable to all countries

Amendment originator:

~~This confidential document is the property of Novo Nordisk. No unpublished information contained herein may be disclosed without prior written approval from Novo Nordisk. Access to this document must be restricted to relevant parties.~~

Table of Contents

	Page
Table of Contents	2
Table of Figures	2
Table of Tables	2
1 Introduction including rationale for the protocol amendment	3
2 Changes	3
2.1 Section 1 Summary.....	3
2.2 Section 2 Flow Chart.....	4
2.3 Section 3.2 Rational for trial design.....	4
2.4 Section 5.1 Type of Trial.....	5
2.5 Section 5.3.5 Patients Continuing Into the Extension Phase.....	5
2.6 Section 8.1.4 Visit 14-n and EOT Visit- visit in the Extension Phase of the trial.....	5
2.7 Section 8.1.8 Transfer of Patients to pathfinder^{TM7}	5
2.8 Section 8.3.2 Antibody assessments.....	6
2.9 Section 8.3.2.3 HCP antibodies	6
2.10 Section 8.3.7 Central Laboratory Assessments.....	7
2.11 Section 8.3.7.3 FVIII Activity (central Laboratory).....	7
2.12 Section 8.4.5. PRO Questionnaires and Health Economics.....	7
2.13 Section 10 Interactive Voice/Web Response System (IV/WRS).....	7
2.14 Section 12.2.1 Follow-up of Adverse Events.....	8
2.15 Section 18.5 Interim Analysis.....	9
2.16 Section 25 Retention of Clinical Trial Documentation and Human Biosamples	9

Table of Figures

	Page
Figure 1 Figure 3-1 Overview of the pathfinder TM clinical trial programme.....	4

Table of Tables

	Page
Table 2–1 Table 12-1 Handling of Not Recovered/recovering Non-Serious AEs from pathfinder ^{TM3}	8
Table 2–2 Table 12-2 Handling of Not Recovered/recovering Non-Serious AEs from pathfinder^{TM7}	9

1 Introduction including rationale for the protocol amendment

This protocol amendment has been prepared to include the following changes to the protocol:

- Allow some parthfinderTM2 patients to participate in a separate PK trial NN7088-4033 (pathfinderTM7). The rationale for conducting the pathfinderTM7 is to compare the PK profile for N8-GP produced at two different manufacturing sites
- Monitor antibody development against Host Cell Protein (HCP). No new blood samples will be required since the samples collected for the N8-GP binding antibody analysis will be used. The rationale for implementing the HCP antibody analysis is based on a recommendation from the U.S. Food and Drug Administration (FDA)
- Interim analysis including data from the extension phase part 2 are planned prior to submission of Biologics License Application and Marketing Authorisation Application
- Prolonged storage of leftover blood samples to enable further characterisation as new biomarkers related to the disease and/or safety, efficacy, or mechanism of action may evolve. This might improve the understanding and treatment of haemophilia in the future.

Furthermore minor mistakes and inconsistencies have been corrected.

In this protocol amendment:

- Any new text is written *in italics*.
- Any text deleted from the protocol is written using ~~strike through~~.

2 Changes

2.1 Section 1 Summary

...

If the patients need to undergo surgery during the present trial they can switch into the surgery trial NN7088-3860 (pathfinderTM3). Upon completion of the surgery the patients can return to the NN7088-3859 (pathfinderTM2) trial.

In some countries patients will have the possibility to participate in a separate PK trial NN7088-4033(pathfinderTM7). If a patient decides to participate in the pathfinderTM7, the patient will return to the pathfinderTM2 trial after completion of the pathfinderTM7.

...

- N8-GP drug product

N8-GP 2000 U/vial 211µg/vial drug product is a lyophilised powder in single use vials with a nominal content of 2000 U/vial produced by Novo Nordisk A/S, ~~Denmark~~.

2.2 Section 2 Flow Chart

...

Footer 12: *Approximately every year* ~~Only yearly~~ (at V21, V25...)

For 'N8-GP binding antibodies' the following footnote is added:

Footer 15: *HCP antibodies will be analysed using samples taken for the N8-GP binding antibodies at the time points described in section 8.3.2.3*

2.3 Section 3.2 Rational for trial design

...

The phase 3 trials are offered as one package to each investigational site to ensure that patients are offered to continue N8-GP until commercially available and patients in need of surgery can undergo surgery without having to switch product. *In addition patients in some countries will be offered to participate in a PK trial NN7088-4033 (pathfinder™7). Patients will return to pathfinder™2 after completion or withdrawal from pathfinder™7.*

...

[figure not shown]

Figure 1 Figure 3-1 Overview of the pathfinder™ clinical trial programme.

2.4 Section 5.1 Type of Trial

...

Recruitment into the surgery trial pathfinderTM3 will begin after successful treatment of bleeding episodes with N8-GP in at least 5 patients in the pivotal trial pathfinderTM2. The surgery trial will not be initiated until at least 20 bleeding episodes in at least 10 patients are treated with N8-GP in the present trial.

In addition patients in some countries will be offered the opportunity to participate in a PK trial (pathfinderTM7). Patients will be allowed to return to pathfinderTM2 after completion or withdrawal from pathfinderTM7.

2.5 Section 5.3.5 Patients Continuing Into the Extension Phase

...

As all patients will complete the Main Phase at the same time the continuation of patients from the Main Phase to the Extension Phase will be gradual and within a window of approximately 2 months depending on approval of the Extension Phase in the country and of patients' next scheduled visit. ~~Please refer to~~

In the Extension phase part 2 patients already included in the pathfinderTM 2 trial will in some countries be offered the opportunity to participate in the pathfinderTM 7 PK trial.

Please refer to Figure 3-1 for an overview of the flow of patients between trials in the clinical development programme.

2.6 Section 8.1.4 Visit 14-n and EOT Visit- visit in the Extension Phase of the trial

...

Blood sampling for central laboratory assessments:

- Biochemistry, see section 8.3.7.1 (not at Visit 14)
- ...
- *Host cell protein (HCP) antibodies, see section 8.3.2.2*

2.7 Section 8.1.8 Transfer of Patients to pathfinderTM7

To enable patients to be transferred to the pathfinderTM7 trial, the Investigator must ensure the following:

- *Order trial product for the pathfinderTM7 to ensure that trial product is available at trial start*

- *At the day of transferring to pathfinder™7 the IV/WRS "PK trial transfer" session must be used in order to transfer the patient into pathfinder™7*
- *The patient must return all drug dispensed in the current trial before entering pathfinder™7*
- *After completion of pathfinder™7 trial the IV/WRS "PK trial transfer session" must be performed in order to transfer the patient into pathfinder™2*

Upon completion of pathfinder™7, patients should return to pathfinder™2 re-entering the treatment regimen as per their prior participation in the trial.

If a patient cannot return to the same treatment regimen as before transferring to pathfinder™7, the investigator must choose the most appropriate regimen for the patient available in pathfinder™2. However, patients in the every 4 day dosing regimen will not be allowed to switch to every 7 day dosing regimen until the 6 month evaluation period have been completed and the requirements fulfilled see section 5.3.1.

The patient will return to the next visit in line in pathfinder™2 and the visit assessments performed at the EOT visit in pathfinder™7, will be used.

2.8 Section 8.3.2 Antibody assessments

...

The samples will be analysed both using the Bethesda assay identifying inhibitory antibodies towards FVIII and using an assay capable of identifying the occurrence of any antibodies towards N8-GP.

In addition an analysis for antibodies developed against HCP, i.e., HCP-antibodies, will be performed. HCP are small pieces of protein remaining from the synthesis of recombinant FVIII in CHO cells. These proteins are removed during the purification, however very small amounts may be present in the drug product and could potentially cause an immune response.

2.9 Section 8.3.2.3 HCP antibodies

A selection of the samples collected for the N8-GP binding antibody analysis will be analysed for HCP antibodies. This analysis will be performed depending on the amount of sample available.

The analysis of HCP antibodies is planned to include samples taken at the following time points: pre-dose prior to first N8-GP exposure and hereafter approximately every 6-12 months.

If deemed necessary more samples may be analysed to fully characterise the individual patient's HCP antibody profile.

2.10 Section 8.3.7 Central Laboratory Assessments

...

For pathfinderTM2 main phase: All blood samples including genotyping blood sample will be destroyed after finalisation of the trial report. ~~Blood samples of patients who are suspected of inhibitors or who have developed inhibitors will be stored at least until evaluation of the clinical trial data by the authorities in the patient's country.~~

For pathfinderTM2 extension phase: Laboratory samples will be destroyed after trial completion.

If allowed by local law and consented to, in pathfinderTM2 extension phase addendum 'Storage of blood samples from pathfinderTM2', samples drawn for analysis of antibodies in pathfinderTM2 main and extension phase will be stored until market authorisation in case further characterisation of the samples should be required by authorities.

However, if allowed according to local law all blood samples might be stored for a maximum of 15 years from end of trial after which they will be destroyed see section 25.2.

2.11 Section 8.3.7.3 FVIII Activity (central Laboratory)

The analysis of plasma FVIII activity will be performed at laboratory selected by Novo Nordisk by ~~two three~~ different assays (*one stage clot and chromogenic assay see below*), but only one FVIII activity result is reported to the site.

2.12 Section 8.4.5. PRO Questionnaires and Health Economics

PROs will be collected at screening visit (Visit 1), *at Visit 13 (end of main phase)*, at Visit 17 (end of part 1) and *approximately every year during Extension Phase part 2 (Visit 21, 25...)* and at the End of Trial visit for all patients.

2.13 Section 10 Interactive Voice/Web Response System (IV/WRS)

...

As a minimum, the system will be used for:

- screening of patients
- ...
- *PK trial transfer session*

2.14 Section 12.2.1 Follow-up of Adverse Events

...

After access to update the AE form in EDC is removed the Investigator must record any SAE and MESI follow-up information, if required, on the paper CRFs provided at trial closure.

Details on how to handle AEs that were not Recovered/Recovering in the pathfinder^{TM3} Surgery & pathfinder^{TM7} PK Trials when patients are ~~included in~~ returning to the pathfinder^{TM2} Trial

An AE (including SAEs and MESIs), that is not recovered/recovering in the Surgical Trial pathfinder^{TM3} when the patient is ~~enrolled into~~ returns to the present trial (pathfinder^{TM2}), will be followed up in the preceding Surgical Trial (pathfinder^{TM3}) and entered by the Investigator as concomitant illness in the present trial. *An AE (including SAEs and MESIs), that is not recovered/recovering in the PK trial (pathfinder^{TM7}) will upon return of the patient be followed up in the present trial (pathfinder^{TM2}).*

Non-serious AEs that are reported as not related and not severe in the Surgery and PK Trials will not be followed-up when ~~enrolling into~~ returning to the pathfinder^{TM2} trial. Details on how to handle unresolved non-serious AEs when patients are transferred from the pathfinder^{TM3} & 7 (Surgery and PK Trials) into the present trial (pathfinder^{TM2}) are described below and in table 12.1 and table 12.2.

Table 2–1 Table 12-1 Handling of Not Recovered/recovering Non-Serious AEs from pathfinder^{TM3}

Severity		Outcome Categories		Relationship		AE follow-up in:	AE in NN7088-3859 (Present)	Concomitant illness in NN7088-3859 (Present)
Mild/Moderate	Severe	Recovered/Recovered with sequelae/Fatal/Unknown	Not recovered/Recovering	Probable/Possible	Unlikely	NN7088-3860 (Surgery)		
X			✗	X		Yes	No*	Yes
	X		✗	X		Yes	No*	Yes
X			✗		X	No	No*	No
	X		✗		X	Yes	No*	Yes

* Unless worsened during participation in pathfinder^{TM2} (Present Trial)

Table 2–2 Table 12-2 Handling of Not Recovered/recovering Non-Serious AEs from pathfinder™7

Severity		Relationship		AE follow-up in: NN7088-4033 (PK)	AE in NN7088-3859 (Present)	Concomitant illness in NN7088-3859 (Present)
Mild/Moderate	Severe	Probable/Possible	Unlikely			
X		X		No	No	Yes
	X	X		No	No	Yes
X			X	No	No	Yes
	X		X	No	No	Yes

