CRF and forwarding these to Novo Nordisk. If for any reason the EDC application is unavailable, then fax, telephone or e-mail to Novo Nordisk.

All SAEs and MESIs must be followed up until the outcome of the event is "recovered", "recovered with sequelae" or "fatal" and until all queries have been resolved. Cases of chronic conditions or cancer or AEs ongoing at time of death (i.e. the subject dies from another AE) can be closed with the outcome of "recovered" or "not recovered". Cases can be closed with an outcome of "recovering" when the subject has completed the trial and is expected by the Investigator to recover.

After access to update the AE form in EDC is removed the Investigator must record any SAE and MESI follow-up information, if required, on the paper CRFs provided at trial closure.

Details on how to handle AEs that were not Recovered/Recovering in the pathfinder™3 Surgery Trial when patients are included in the pathfinder™2 Trial

An AE (including SAEs and MESIs), that is not recovered/recovering in the Surgical Trial pathfinder™3 when the patient is enrolled into the present trial (pathfinder™2), will be followed up in the preceding Surgical Trial (pathfinder™3) and entered by the Investigator as concomitant illness in the present trial.

Non-serious AEs that are reported as not related and not severe in the Surgery Trial will not be followed-up when enrolling into the pathfinder™2 trial. Details on how to handle unresolved non-serious AEs when patients are transfer from the pathfinder™3 (Surgery Trial) into the present trial (pathfinder™2) are described below and in [Table 12-1](#).

A not recovered AE from the preceding Surgery Trial which has worsened during participation in the pathfinder™2 must be entered as an AE in the present pathfinder™2 by the Investigator.

Table 12-1 Handling of Not Recovered Non-Serious AEs from pathfinder™3

Severity		Outcome Categories		Relationship		AE follow-up in: NN7088-60 (Surgery)	AE in NN7088-3859 (Present)	Concomitant illness in NN7088-3859 (Present)
Mild/ Moderate	Severe	Recovered/ Recovered with sequelae/ Fatal/ Unknown	Not recovered/ Recovering	Probable/ Possible	Unlikely			
X			X	X		Yes	No*	Yes
	X		X	X		Yes	No*	Yes
X			X		X	No	No*	No
	X		X		X	Yes	No*	Yes

* Unless worsened during participation in pathfinder™2 (Present Trial)

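### Protocol 12.2.1: three of the four rows of Table 12-2 conflict with the text on following up unresolved non-serious AEs carried over from the PK trial

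*Protocol*

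**What the plan says.** Amendment 19 allows some patients in part 2 of the Extension Phase to enter a PK trial (pathfinder 7) and then return. It revised section 12.2.1 for AEs unresolved at that point.

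- **Text, general rule.** For an AE not resolved in the PK trial, with SAEs and MESIs expressly included, the event "will upon return of the patient be followed up in the present trial".
- **Text, exemption.** The next paragraph says: "Non-serious AEs that are reported as not related and not severe in the Surgery and PK Trials will not be followed-up" when the patient comes back to pathfinder 2. It then points to Tables 12-1 and 12-2 for the details.
- **Table 12-2 (PK trial).** Its scope is "Handling of Not Recovered/recovering Non-Serious AEs". All four combinations of severity and relationship carry the same three entries: AE follow-up in the PK trial, No; AE in the present trial, No; concomitant illness in the present trial, Yes.
- **Table 12-1 (surgery trial).** The three severe or related rows have AE follow-up Yes in the surgery trial and concomitant illness Yes. The mild/moderate unrelated row has No for both. The column for an AE in the present trial is No with a footnote: "Unless worsened during participation in pathfinder" 2.

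Amendments 20 and 21 do not change section 12.2.1.

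**The concern.** The text assigns follow-up of severe or related events to the present trial. The table shows AE follow-up of those events in neither trial. A site is likely to work from the table, because the text names it as the place for the details.

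What is at stake is the outcome of such events. The protocol defines outcome categories for AEs, and since Amendment 6 it requires non-serious AEs to be followed until an outcome is reached or the follow-up period ends. It states no corresponding outcome rule for concomitant illness. In addition, Section 11 ties the recording of concomitant illness to the first visit or re-entry from the surgery trial. Amendment 19 did not extend it to re-entry from the PK trial.

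**Working it through.** No arithmetic beyond a row count applies. The inputs are the two text rules and the two tables in section 12.2.1 as amended, plus the general AE rules in sections 12.1 and 12.2.1.

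**Step 1: what the text requires by row.** The exemption needs both conditions, unrelated and not severe. The protocol's relationship scale is probable, possible or unlikely, so I take unrelated to mean the unlikely column. One of the four cells is exempt, and 4 − 1 = 3 cells fall under the general rule.

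**Step 2: compare with Table 12-2.** Entries are in the order PK follow-up / AE in present trial / concomitant illness.

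| Row | Text | Table 12-2 | Agreement on AE follow-up |
|---|---|---|---|
| Mild/moderate, probable or possible | follow in present trial | No / No / Yes | conflict |
| Severe, probable or possible | follow in present trial | No / No / Yes | conflict |
| Mild/moderate, unlikely | not followed | No / No / Yes | agrees |
| Severe, unlikely | follow in present trial | No / No / Yes | conflict |

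Three of four rows conflict. The mild/moderate unrelated row agrees on AE follow-up. Its concomitant-illness entry differs only from the corresponding row of Table 12-1, not from the text.

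**Step 3: compare with Table 12-1.** For the surgery trial, the text keeps follow-up in the originating trial and adds a concomitant-illness entry, with the same exemption. Table 12-1 gives Yes / No* / Yes in the three severe or related rows and No / No* / No in the exempt row, where the asterisk is the worsening footnote. That table matches its text in all four rows. It also treats AE follow-up and concomitant illness as different things, each with its own column.

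**Step 4: what other rules already cover.**
- SAEs are outside Table 12-2. Section 12.2.1 requires SAEs and MESIs to be followed to outcome. A non-serious MESI falls within the table's literal scope, but that general rule still applies to it.
- Section 12.1 requires a worsening of a concomitant illness to be recorded as an AE. Every row of Table 12-2 is entered as concomitant illness, so worsening is covered even though this table has no footnote. The specific worsening sentence in section 12.2.1 names only one source: "A not recovered AE from the preceding Surgery Trial which has worsened during participation in the pathfinder" 2.

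What remains uncovered is an ongoing, non-worsening, non-serious AE that is severe, related or both.

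**The case against.** The strongest reply is that text and table can be read together. No in the PK-trial column fits the text, which moves follow-up to the present trial. No in the present-trial AE column could mean only that no new AE form is opened, which is how Table 12-1 uses that column. Table 12-2 has no separate column for continued follow-up in the present trial, so it does not expressly rule it out.

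That last remark stands, but the reading does not resolve the conflict. With No in both AE columns, the only place left for follow-up is the concomitant-illness entry. Table 12-1 shows that the protocol does not equate the two. All four rows would also then be handled alike, and the exemption in the text would have no effect.

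Other parts of the reply do limit the consequences:
- Severity and relationship were already assessed in the PK trial, so only the later outcome is at risk.
- Amendment 6 removed the stricter rule for severe or related non-serious AEs. Any non-serious AE may now stop at recovering or at the end of the follow-up period.
- The SAP summarises treatment-emergent AEs by frequency, severity and relationship. It states no summary that depends on final outcome.
- Section 11 does not list every field of the concomitant-illness form, so it cannot be shown that the form omits outcome.
- The closure rules of the PK trial are in a protocol that is not available here.

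**Conclusion.** The text and Table 12-2 conflict in three of four rows, and the conflict is in current text. For ongoing, non-worsening, non-serious AEs in those rows, the outcome may be tracked as an AE in neither trial. This rests on two assumptions: that sites follow the table, and that the PK trial does not itself keep such events open after the patient leaves. The number of patients affected is not given.

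A reader might infer more, and the documents do not support it:
- **Serious events are lost.** Severe is an intensity grade and the table is limited to non-serious AEs. SAEs and MESIs must be followed to outcome.
- **All four rows are wrong.** The mild/moderate unrelated row agrees with the text on AE follow-up.
- **Worsening events go unreported.** The general rule in section 12.1 covers them.
- **The long-term safety objective of part 2 is weakened.** No planned analysis is shown to depend on the missing outcomes.

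The point is a wording inconsistency that affects what sites do. It is worth correcting and limited in reach.

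**What to change.** Reconcile Table 12-2 with the text of section 12.2.1, so that it shows in which trial severe or related unresolved non-serious AEs are followed to outcome. For consistency, carry over the worsening footnote from Table 12-1. The mild/moderate unrelated row needs no change on AE follow-up. The sponsor may wish to state whether its concomitant-illness entry is meant to differ from Table 12-1. Section 11 could name re-entry from the PK trial at the same time.

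The cost is one corrected table and a notice to sites. No new data forms are needed.
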